Two pilot intervention groups with Veterans will be conducted during this phase. Groups will be audio-recorded. The PI will train and work with a psychology trainee or research staff to facilitate groups in this study phase. The PI will train all group facilitators via mini-workshops prior to conducting groups in which all intervention materials will be reviewed and discussed. Several assessment measures will be completed at the start of each session (see Assessment section). At the end of each session, Veterans will complete satisfaction ratings and provide feedback. Group facilitators will also provide ratings and feedback at the end of each session.

The intervention developed as part of this project is conceptualized as being the first stage in a stepped care approach. As such, Veterans will be recruited from the PTSD and Geriatric Mental Health Clinics if they are: new patients, established patients who have declined or dropped out of more structured trauma-focused therapy, have partial PTSD, or if they are deemed inappropriate for trauma-focused therapy due to health impairments. Following post-group assessments, if any participants are still reporting significant symptoms and distress and indicate interest, they may be referred to other groups within one of the VA clinics or to trauma-focused EBPs such as Prolonged Exposure or Cognitive Processing Therapy or other EBPs (e.g., CBT for Insomnia). Veterans will be provided with descriptions of a variety of evidence-based treatment options, and will be given referrals as appropriate. Veterans' attitudes about mental health treatment and readiness to change will be examined before and after group participation.

Groups will be conducted during regular business hours. [name] (the PI) is a licensed clinical psychologist, and will be available during screening calls, baseline and follow-up assessments, and during group sessions in case of a clinical emergency. If needed, the PI will be contacted to conduct a risk assessment with a patient, and if it is determined that immediate care is needed, will walk the participant down to urgent care. The PI will also have referral information and important resources (e.g., the Veteran's crisis line, suicide prevention coordinator numbers) available. In the event that the PI is not available to provide clinical coverage, another licensed provider will be asked to provide coverage.

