Activity 3: Following data analysis, a manuscript detailing the results of the study will be prepared. In addition, final revisions will be made to the intervention protocol according to group member and facilitator feedback, expert panel suggestions, as well as lessons learned in this phase of the study. To evaluate the utility of the intervention in preparing Veterans for trauma-focused therapy, utilization of mental health treatment will be assessed at the six month follow-up.

Finally, data collected as part of this study will be used as pilot data (including effect size estimates for power calculations) in the development of a possible VA Merit award submission to conduct a RCT of the group intervention.

Recruitment and Participant Characteristics:

- For both the intervention and support groups, recruitment of Veteran participants will be conducted in the manner used in Phase II.
- For all groups, approximately 14 participants will be recruited (target group membership is 10 participants per group).

Inclusion/Exclusion Criteria: For both the intervention and support groups, inclusion/exclusion criteria for Veteran participants will be the same as used in Phase II of this study. In addition, participants of Phase II will be excluded from participation in Phase III.

Procedure: This procedure will be the same as followed in Phase II. Those Veterans who are eligible to participate will be randomized in groups of 3 (block randomization) to participate in either an intervention group or a support group. Three intervention groups and support groups will be conducted during this phase. All groups will be conducted by doctoral level psychologists or psychology trainees or research staff who the PI will have trained. Given that this is a small study, there is a limited number of available group facilitators, and therapeutic allegiance effects are not expected, group facilitators will conduct either intervention groups or support groups. All groups will be audio recorded. Several assessment measures will be completed at the start of each session. At the end of each session, Veterans will complete satisfaction ratings and provide feedback. Veterans in both conditions (intervention and control) will be given between-session assignments that will be collected. Fidelity to the intervention and support group protocols will be monitored by a doctoral

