level psychologist who is not part of the study team and is familiar with cognitive-behavioral interventions for PTSD. Each group session will be digitally recorded, and the monitor will listen to a randomly selected sample (20% of the sessions) and complete a fidelity monitoring form. Group facilitators will also provide ratings and feedback at the end of each session. Following the last session, Veteran participants will be asked to complete post-group assessment measures. Veterans will be asked to complete follow-up assessments at one month and six months, either via postal mail or in person.

Consistent with the recruitment method followed in Phase II, Veteran participants for both the intervention and support groups will be recruited from the PTSD and Geriatric Mental Health Clinics if they are new patients, if they are established patients but have declined or dropped out of more structured trauma-focused EBPs, if they have partial PTSD, or if they are deemed inappropriate for trauma-focused therapy due to health impairments or other reasons. The same procedure will be followed as in Phase II after the six month follow-up. Specifically, Veterans will be presented with descriptions of a variety of evidence-based treatments, including trauma-focused EBPs, and provided with referrals should they request them. Attitudes toward treatment and readiness for change will also be assessed. In addition, the VA electronic medical records will be reviewed to document enrollment and completion of mental health treatment at the six month follow-up.

Groups will be conducted during regular business hours. [name] (the PI) is a licensed clinical psychologist, and will be available during screening calls, baseline and follow-up assessments, and during group sessions in case of a clinical emergency. If needed, the PI will be contacted to conduct a risk assessment with a patient, and if it is determined that immediate care is needed, will walk the participant down to urgent care. The PI will also have referral information and important resources (e.g., the Veteran's crisis line, suicide prevention coordinator numbers) available. In the event that the PI is not available to provide clinical coverage, another licensed provider will be asked to provide coverage.

For each group session attended we will provide compensation (\$10) for travel, a practice that is consistent with VA policy to reimburse for travel expenses for VA appointments for service-connected conditions.

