After the final session, a booster or follow-up session will be scheduled for 1 to 3 months following the end of the 9-session group. The purpose of this session is to check-in with group members, discuss treatment gains and current symptoms, and to provide referrals and resources as appropriate. Veterans will also receive \$10 for attending this session.

Procedures implemented during the Coronavirus Pandemic

In light of the current COVID-19 pandemic, we will be transitioning all study-related in-person procedures to a virtual telehealth format, as follows:

Procedure

Recruitment

Veteran recruitment will remain the same as described above in Phase III for in-person groups.

Obtaining Consent & Baseline Appointments

Veterans who indicate interest in the study will receive a screening call from a study staff member. A revised HIPAA waiver has been submitted to allow the collection of PHI (month/year of birth, name, email, and last 4 of SSN) during the screening call, prior to completion of the combined ICF/HIPAA. This is different from the previously approved HIPAA waiver, as we are collecting each Veteran's email address in order to send them the link to the video appointments, as well as replacement study materials as needed (please see page 18). If potential Veteran participants are interested in the study and meet preliminary eligibility criteria during the screening call, they will be sent an envelope

in the mail with a cover letter, the ICF/HIPAA document, and all baseline measures except the SCID. A pre-addressed, stamped envelope will be included to facilitate return of all documents to study staff. It will be emphasized over the phone during the screening call that participants should not begin the baseline measures until they have completed the informed consent documents with study staff.

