All Veterans who participate in Phase II and Phase III (intervention group pilot testing and comparison of group intervention with support group) will complete a structured diagnostic interview, baseline assessments, satisfaction ratings of each session, and post-group assessments. Phase III participants will complete one and six month follow-up assessments. Participants will be remunerated for their time and inconvenience. Baseline assessments (including the SCID questions) are estimated to take about 90 minutes and participants will be compensated \$20 for completion. Post-group and follow-up assessments are estimated to take 1 hour and participants will be compensated \$35 for each assessment they complete (Phase III participants will receive \$40 for completion of the six month follow-up). Additionally, all participants in Phases II and III will be remunerated \$10 to cover travel expenses for each group session they attend. Thus, Veterans who participate in Phase II could receive up to \$155 total and Veterans who participate in Phase III could receive up to \$230 total.

In case of a lapse between the time of baseline and the start date of the cohort, we may decide to reassess the participant and recomplete the baseline appointments. If the Veteran has a SCID lifetime rating, the SCID does not have to be recompleted; otherwise, both the SCID and the measures will be re-administered. In the event that this is the case, we will pay participants \$20 for their recompletion of the baseline.

Measures (see Table 2)

Note: This proposal is being written after publication of DSM-5 but prior to the release of appropriately updated assessment measures. Revised versions of all assessment measures that are available at the time the study is conducted will be used.

Phase IA: This is the protocol development phase. No participants will be enrolled or assessment measures collected during this phase.

Phase IB: Prior to being invited to participate in the focus groups for Veterans, potential participants will be screened over the telephone with the PC-PTSD-5.

All focus group participants will be contacted by telephone after attending the focus groups and asked several open-ended questions to gather feedback and allow participants a chance to share comments they may not have felt comfortable disclosing during the focus groups themselves.

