the study. Three intervention groups of up to 14 Veterans each, as well as three comparison support groups will be conducted during this phase. Approximately 84 participants will be recruited for these groups. Veteran participants will be recruited from a) flyers posted at each VA Boston Healthcare System location, b) flyers and information given to clinicians within the PTSD clinics, the Geriatric Mental Health Clinic, and medical clinics, c) contacting Veterans seen in the PTSD clinic who indicated interest in research d) word of mouth from other participating Veterans, and e) a roster of Veterans who have sought services through the VA National Center for PTSD and have indicated consent to be contacted for other research studies. Inclusion criteria: Veterans need to be at least 60 years old to be eligible to participate in the study. For both intervention and support groups, participants (who will be assessed with the PTSD questions from the SCID prior to being invited to participate), must endorse a military-related criterion A event, at least one intrusion symptom (cluster B), one symptom of avoidance (cluster C), one symptom related to negative alterations in cognition or mood (cluster D), one symptom related to alterations in arousal or reactivity (cluster E), and report of impairment in functioning (cluster G; DSM-5). Exclusion criteria: Veterans who are in current treatment for PTSD, are diagnosed with a psychotic disorder or have psychotic symptoms, have been hospitalization for suicidal ideation or psychosis within the past year, or have a diagnosis of dementia or other severe cognitive disorder. Veterans will be asked not to join therapy groups or other interventions for the duration of their participation in the study. Potential participants will also be excluded if they do not agree to be audio recorded. In addition, Veterans who participated in the pilot phase of the study will be excluded from participating in the comparison condition phase.

(b) Sources of materials.

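### Treatment uptake at six months has VA records as its only named source, although Veterans outside the VA may enrol and the statements on referral and other therapy conflict

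*Combined protocol and SAP*

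**What the plan says.** All references are to the combined protocol and SAP.

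- **Purpose and timing.** Phase III, Activity 3, evaluates how well the intervention readies Veterans for trauma-focused treatment, and for this "utilization of mental health treatment will be assessed at the six month follow-up". It serves the complementary objective in section (1)(b), which includes engagement in evidence-based psychotherapy.
- **Source.** Phase III, Procedure: "the VA electronic medical records will be reviewed to document enrollment and completion of mental health treatment at the six month follow-up". No second source is named there.
- **Population.** The Human Studies Section, under the comparison condition, admits community Veterans who are not VA users.
- **Other therapy.** The same section states: "Veterans will be asked not to join therapy groups or other interventions for the duration of their participation in the study". The length of participation is not defined. Under Assessments and Participant Compensation, "Phase III participants will complete one and six month follow-up assessments".
- **Referral.** In Phase II, Procedure: "Following post-group assessments, if any participants are still reporting significant symptoms and distress and indicate interest, they may be referred to other groups". In Phase III, Procedure: "The same procedure will be followed as in Phase II after the six month follow-up". Veterans are then given descriptions of treatments, trauma-focused ones included, and are "provided with referrals should they request them". The Phase III booster, one to three months after the group ends, is held to "discuss treatment gains and current symptoms, and to provide referrals and resources as appropriate". The pandemic procedures (Post-Assessment and Follow-Ups) place clinical referral after participation is over. The Human Studies Section, under Protection against risk, lets the PI refer a distressed participant, with no limit on timing.
- **Measures and analysis.** Neither the measures text nor Table 2 lists a self-report of treatment use, and the Phase III Data Analysis Plan does not mention utilization.

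**The concern.** Attitudes and readiness are covered by the EASI and URICA in Table 2. Utilization is the only named measure of whether Veterans actually enter treatment, and study data may feed the design of a later randomized trial.

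As written, a low recorded figure would have several explanations besides lack of preparation. The Veteran may have been treated outside the VA. He may have been doing what the study asked. Or the referral that would have led to treatment may not yet have been made. The plan collects nothing that would separate these.

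**Working it through.** **1. Source against population.** VA records show VA care. A Veteran who is eligible without using the VA, and who starts treatment elsewhere, would be counted as having started none. The documents do not give the share of such Veterans.

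**2. How long participation lasts.** The stated Phase III maximum payment is $230. Inputs: baseline 20, post-group 35, one-month 35, six-month 40, and 10 for each of nine sessions plus the booster.

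20 + 35 + 35 + 40 + (10 × 10) = 230, which reproduces the plan's figure.

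For payment, then, participation includes the six-month assessment. This makes it plausible that the request about other therapy also runs to six months, but no sentence says so.

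**3. Time for a referral to show in a review at six months.** Assume that six months is counted from the last session.

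| Where the text places referral | Months left before the review |
|---|---|
| After the six-month follow-up (Phase III, Procedure) | 6 − 6 = 0 |
| After participation ends (pandemic procedures), if that means the six-month assessment | 0 |
| Booster at 1 to 3 months | 6 − 3 = 3 to 6 − 1 = 5 |
| For distress (Protection against risk) | Any; no timing given |

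**4. The request read two ways.**

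- *It ends with the group sessions.* Booster referrals are compatible with it, and about six months are open for uptake. The restriction then matters little.
- *It runs to six months.* A Veteran who joins an intervention on a booster referral departs from the request. Recorded uptake before six months then partly measures departure from the request.

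The text does not settle which reading applies.

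**5. Effect on the comparison of arms.** Let p₁ and p₂ be true uptake in the two arms, and s₁ and s₂ the fractions of it that the records show by six months. The recorded difference is s₁p₁ − s₂p₂.

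- If s₁ = s₂ = s, it equals s(p₁ − p₂): smaller than the true difference whenever s is below 1, with the same sign.
- If s₁ ≠ s₂, a difference of p(s₁ − s₂) appears even when p₁ = p₂ = p.

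The request, the booster, the referral step and the record source are the same in both arms, so the first case is the natural one. The documents give no value for p or s, so neither the dilution nor any bias can be put in figures.

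**6. Scale only.** Planned arms are 3 × 10 = 30 at target group size, or 84 / 2 = 42 on planned recruitment (also 3 × 14 = 42). One Veteran is 100/30 = 3.3 or 100/42 = 2.4 percentage points. That is the step size of any proportion in arms this small, not an estimate of the effect.

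**The case against.** **The timing may be deliberate.** A reader might infer from the zero in the table that a six-month review cannot detect uptake, or comes at the wrong time. The documents do not support that. The zero applies only to referrals made after six months. Booster and distress referrals can come earlier, Veterans may seek care themselves, and documenting enrollment and completion implies looking back over earlier treatment. Measuring uptake before an end-of-study referral offered to both arms is also defensible, because it keeps the group's effect apart from the effect of that offer.

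**The restriction is inferred to be long.** The plan describes the intervention as the first step of stepped care and gives referrals at the booster. Both fit a request limited to the group period. This stands, so the compliance explanation is conditional.

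**Absence from Table 2 proves little.** The table also omits demographics, which are collected, and the measures text does not describe every instrument listed. Part of the protocol after the heading Work Accomplished, and the consent pages, were not available. The finding is therefore limited to the available text.

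**Non-VA care may be uncommon.** Most recruitment routes are VA clinics, campuses and rosters, and VA records suit VA-referred care. That is fair, but the plan opens enrolment to non-users and gives no means of seeing their treatment.

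**Utilization carries little weight in the plan.** It is absent from the Phase III research questions and analysis plan, and the study is a small pilot. This limits the severity; it does not resolve the conflicting statements.

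**Conclusion.** The point holds and is minor. Two things are established from the text: the only named source would miss non-VA care in a population that may include Veterans outside the VA, and the statements on referral and on other therapy do not agree about what a Veteran may do, and when, before six months. One thing is conditional: if the request lasts to six months, low uptake could reflect compliance.

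A reader might infer that the comparison between arms is biased. The documents do not show that; bias would need compliance or non-VA use to differ by arm. The supported conclusion is mainly dilution, of a size that cannot be computed. The 3 to 5 months after a booster referral assume that six months is counted from the last session. The primary outcomes (psychosocial functioning and quality of life) and secondary outcomes (PTSD and depressive symptoms) are not what this point concerns.

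**What to change.** 1. **Reconcile the text.** Bring Phase III, Procedure; the booster paragraph; the pandemic procedures; the comparison-condition text; and Protection against risk into agreement on how long the request lasts and when referrals are made. The choice is the sponsor's.
2. **Add a self-report item.** Put a short question on VA and non-VA mental health treatment, naming trauma-focused therapy, into the existing six-month packet. Report utilization by arm from records and from self-report, showing the source.
3. **Fix the record window.** Use one look-back for every randomized Veteran in both arms, drop-outs included, from the last scheduled session of his group to six months. Anchoring it to a scheduled date avoids dependence on who asked for a referral.

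A later record review is optional. It would delay the result and require a check that consent and record access extend that far.

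The cost is protocol wording and one item in a packet already sent. The downside is uneven data: non-responders, and any cohort already followed up when the item is added, would have records only. The pandemic section describes moving in-person procedures to telehealth, so some groups may already have run. The record-only result should therefore be shown for everyone alongside the combined one.

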Groups will be conducted using a telehealth platform that has options for video and telephone-only participation (such as WebEx). Participants will be sent email invitations that contain links to join the sessions. Video sessions will start 10 minutes prior to the session start time, to provide participants enough time to work through any technological issues with study staff prior to the start of the sessions. Study participants will be asked to provide verbal consent to participating in the virtual telehealth sessions at the start of the first session, after being informed about the limits of confidentiality and important safety issues. The participants will be reminded of these issues at the beginning of the remaining sessions, but will not be verbally re-consented each week. Additionally, participants will be reminded that the session is being audio-recorded. The study PI, a licensed psychologist, or another licensed clinician will be available by phone following the sessions in case any of the participants indicate experiencing distress. Veterans will receive \$10 per session that they attend. Payments will be mailed via check through the agent cashier at two timepoints: after session 4, and after session 9.

Prior to the start of group sessions, participants will be sent a package of all assessments to be completed in sessions, along with a pre-addressed, stamped envelope. Assessment measures will be clearly labeled with Veteran ID, session #, and whether the measure is to be completed at the start or at the end of the group session. During each session, group leaders will facilitate the completion of measures at the start and the end of each group session, and participants will be asked to indicate when they have finished measures and placed them in the included envelope to be returned at the end of the 9 weeks. Study staff will send replacement assessment measures as needed, through postal mail or e-mail.

Post-Assessment and Follow-Ups

Following the last session, Veteran participants will be asked to complete post-group assessment measures (which will be mailed to them). The follow-up booster session will also be conducted over a telehealth platform. Veterans will be asked to complete follow-up assessments at approximately

one month and six months via postal mail. Appropriate clinical referrals will be provided following the end of study participation.

Technical Assistance

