Phase II: Veteran participants will be asked to monitor or rate their use of various strategies at the beginning of each group session. For example, participants will be asked to report on social activities and time spent with friends and family and to rate their use of anger management strategies, coping skills, and relaxation strategies. Several additional behavioral ratings will also be administered. Participants will be asked about the number of nightmares, flashbacks, and hours slept the previous week. They will also be asked about frequency of anger outbursts and will provide a rating of their current distress. As a global process measure, participants will be asked to rate the extent to which they are doing better or worse than the previous session. Additionally, they will be asked to provide satisfaction ratings at the end of each group session. Satisfaction will be rated using several items (e.g., how relevant did today's group feel to you?) with Likert-type response scales (e.g., 1 = *not at all* to 4 = *very*). In addition, Veteran participants will be given the opportunity to provide open-ended comments at the end of each session. Participant treatment engagement will be evaluated by monitoring session attendance, compliance with assignments, and level of participation in group sessions.

Phase III: The measures used in this phase will be the same as used in Phase II, except that the scales used at baseline and post-group will also be administered at follow-up assessments (one and six months).

Limitations to be Addressed in Current Study

As with any study that evaluates a treatment outcome intervention, it is important to anticipate and attempt to minimize problems related to drop-out. For each of the group interventions (pilot, intervention, and support groups), several precautions will be taken to minimize drop-out. Group members will receive a schedule at the start of the group with the dates and times of each group session. Participants will also be given a binder in which to keep all group-related materials. The group schedule will be put in the front of this binder. At the end of each group session, all members will be given an appointment card with the details of the next group session date, time, and location (as well as contact information for group facilitators) on it. Additionally, participants will receive weekly reminder calls from one of the group

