facilitators. Finally, all group members will be given the option of receiving a mid-week telephone check-in with one of the group facilitators. Despite these measures, there will inevitably be some drop-out that occurs during the study. When this occurs, group facilitators will contact the Veteran to explore reasons for discontinuing their participation in the study. This information will be used to inform future phases of the study and future work. Full information maximum likelihood estimation techniques will be utilized when analyzing data and intent-to-treat results will be examined to account for the missing data due to drop-out.

Limitations to be Addressed in Future Research

The overall sample size for the current study is fairly small. However, this study will address questions of feasibility and satisfaction with/acceptance of the developed intervention protocol. Additionally, it will provide preliminary comparisons between the intervention protocol and support groups and provide effect size estimates and information about the group size needed for larger studies. The data gathered from this study will serve as pilot data for a larger randomized clinical trial to be conducted in the future.

Another limitation of the current study is that it is focused on older male Veterans with PTSD. Future research may use the intervention protocol developed in the current study to test the effectiveness with other populations (such as with older women Veterans or with younger Veterans with PTSD).

Table 2. Assessment Measures

Domain	Veteran Pilot Groups (Phase II)				Veteran Intervention/Support Groups (Phase III)					
	Screening	Baseline	All Group Sessions	Post-Group	Screening	Baseline	All Group Sessions	Mid-Group	Post-Group	Follow Up Assessments
Screening										
Structured Clinical Interview for DSM Disorders (SCID) – PTSD Questions only	x				x					
Primary Outcome										
The Quality of Life Inventory (QOLI)		x		x		x			x	x
The Inventory of Psychosocial Functioning (IPF)	x		x		x			x	x	
Veterans RAND 12-item Health Survey (VR-12)	x		x		x			x	x	
Additional Outcome										
Depression, Anxiety, Stress Scales (DASS-21)	x		x		x			x	x	
Sense of Mastery	x		x		x			x	x	
Posttraumatic Stress Disorder Checklist (PCL)	x		x		x			x	x	
Beck Depression Inventory (BDI-II)	x		x		x			x	x	
Other										
Endorsed and Anticipated Stigma Inventory (EASI)		x		x		x			x	x
University of Rhode Island Change Assessment Scale (URICA)		x		x		x			x	x

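### In the Phase III telehealth groups, session forms come back in one envelope after nine weeks with no retrieval from early leavers, so satisfaction and feedback data may be lost and may look too favourable

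*Combined protocol and SAP*

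**What the plan says.** The telehealth procedure stands under Procedures implemented during the Coronavirus Pandemic, Group Sessions, within Phase III. Before the first session, "participants will be sent a package of all assessments to be completed in sessions, along with a pre-addressed, stamped envelope". Forms are filled in at the start and end of each session, and participants indicate when they have finished and "placed them in the included envelope to be returned at the end of the 9 weeks". The only other handling rule is for blanks: "Study staff will send replacement assessment measures as needed, through postal mail or e-mail". The Use of Email section has Veterans told not to reply to study e-mails, so e-mail is not a return route.

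What the forms carry:
- Phase III Procedure: "At the end of each session, Veterans will complete satisfaction ratings and provide feedback".
- Measures to be Completed by Veterans at Each Group Session: "Veteran participants will be asked to monitor or rate their use of various strategies at the beginning of each group session", with open-ended comments at the end. This is the Phase II text, and the Phase III paragraph carries the same measures forward.
- Table 2 lists satisfaction ratings and activity/skills forms at all Phase III group sessions.

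Payment is per session attended, with no link to return of forms: "Payments will be mailed via check through the agent cashier at two timepoints: after session 4, and after session 9". Under Limitations to be Addressed in Current Study, facilitators contact Veterans who drop out to learn their reasons. Asking for completed forms is not mentioned.

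On use of the data, Limitations to be Addressed in Future Research states that "this study will address questions of feasibility and satisfaction with/acceptance of the developed intervention protocol". Phase III Activity 2 uses group members' and facilitators' feedback to revise the intervention.

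**The concern.** A Veteran who leaves after a few sessions has already rated those sessions, but his forms are at home in an envelope that is not due until week 9. When groups meet in person, the same forms are completed in the room and could be handed in on the day. The telehealth rule therefore adds a way to lose data that already exist, and it makes the loss depend on whether the Veteran stays. A single lost envelope also removes a completer's full nine sessions.

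The plan guards against this kind of loss elsewhere. In the telehealth baseline process, the interview appointment does not go ahead until the mailed consent and survey documents have arrived. Session forms have no such check.

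At stake are the Phase III satisfaction data and the comments that inform the final revision. Comments from Veterans who left are especially useful for that purpose and are the most exposed. Full information maximum likelihood does not help: the Phase III models are specified for the primary and secondary outcomes, and no missing-data approach is given for session ratings. The planned comparison of completers with drop-outs cannot use session forms that never arrive.

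**Working it through.** **The plan's own figure.** Three intervention and three support groups of 14 give 6 × 14 = 84, which reproduces the stated Phase III recruitment total. The target membership of 10 per group gives 6 × 10 = 60.

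**Inputs from the documents.** Nine sessions; 14 recruited and a target of 10 per group; example satisfaction items scored 1 to 4.

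**Inputs not in the documents, assumed here.** The drop-out rate, the number of sessions attended before leaving, the share of leavers who never post the envelope, and the gap in mean rating between completers and leavers. For illustration only, the margin of 14 over 10 is taken as 4 leavers.

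**Formula.** Call the start and end forms of one session a session set. With 10 completers, 4 leavers and *k* sessions attended before leaving, the completed sets number 10 × 9 + 4*k*. If no leaver posts the envelope, the share lost is 4*k* / (90 + 4*k*). If completers average *M* and leavers *M* − gap, the mean over all completed sets is *M* − gap × share lost, while the mean over returned sets is *M*. The upward shift is gap × share lost.

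| Sessions before leaving | Sets lost | Shift, gap 0.5 | Shift, gap 1 |
|---|---|---|---|
| 1 | 4 of 94 = 4.3% | 0.02 | 0.04 |
| 3 | 12 of 102 = 11.8% | 0.06 | 0.12 |
| 6 | 24 of 114 = 21.1% | 0.11 | 0.21 |

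**Sensitivity, leaving after three sessions.**
- Lower drop-out: at 10%, the share lost is 0.1 × 3 / (0.9 × 9 + 0.1 × 3) = 0.3 / 8.4 = 3.6%, and the shift is 0.02 (gap 0.5) to 0.04 (gap 1).
- Partial return: if 2 of the 4 leavers post the envelope, 6 of 102 sets (5.9%) are lost. The shift is gap × (12/102 − 6/96) = gap × 0.055, or about 0.03 to 0.06.
- No gap: the shift is 0, though sets are still lost.
- Leavers more satisfied by 0.5: the shift is −0.06.

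**A lost completer envelope.** Nine session sets go at once, which is 9 × 2 = 18 start-of-session and end-of-session completions, with no assumption about satisfaction.

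**The case against.** The strongest reply is that the plan states a collection route, not a loss. The envelope is already addressed and stamped, nothing stops a leaver from posting it, and facilitators contact those who drop out. Weekly reminder calls and optional mid-week check-ins add further contact. Aim 3 ties acceptability and satisfaction to the Phase II pilot groups, whose procedure is written as in person. The Phase III research questions are comparative, and its analysis plan contains no analysis of satisfaction. Attendance, facilitator ratings, audio recordings and reasons for leaving reach the study without the envelope, and the primary and secondary outcomes are collected separately at baseline, post-group and follow-up.

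Much of this stands and limits the point to Phase III telehealth groups, whose number is not given, and to participants' session forms. It does not remove the gap. The statement on satisfaction and acceptance is study-wide, Phase III feedback drives the final revision, and no step asks a leaver for his forms.

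Three stronger readings are tempting and not supported:
- A reader might infer that acceptability is overstated as a matter of fact. That needs both non-return by leavers and lower ratings among them, and the documents give neither.
- A reader might take (14 − 10)/14 = 28.6% as expected drop-out and, with a 1-point gap, claim an overstatement of 0.29. The plan does not call that margin in-treatment drop-out. It may include Veterans lost before session 1, and the Human Studies Section allows intervention groups of up to 14. The 0.29 also counts each leaver as a full participant, whereas only forms completed before leaving are at risk.
- A reader might infer that distress ratings go unmonitored, since in the Phase II text Veterans "will provide a rating of their current distress". The plan nowhere says that in-person ratings are read in real time, and a licensed clinician is available by phone after telehealth sessions. Table 2 as extracted puts the Phase III behavioral PTSD ratings at baseline, post-group and follow-up, although the table may be broken.

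**Conclusion.** The concern holds as a conditional weakness in data collection. Holding every session form until one return at week 9, with no retrieval from early leavers, puts completed ratings and comments at avoidable risk. Phase III satisfaction and the revision feedback may look too favourable if less satisfied Veterans leave and keep the envelope. In the central illustration about 12% of completed session sets are lost and the mean moves by roughly a tenth of a point or less. The loss figure rests on assumed drop-out, timing and non-return. The shift rests on an assumed rating gap as well, and vanishes or reverses without one. The treatment comparison on the primary and secondary outcomes is not affected. The point is worth acting on because the remedy is cheap and no later analysis can recover forms that never arrive.

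**What to change.** In the telehealth Group Sessions text, make three changes:
1. Supply a second pre-addressed, stamped envelope, and ask for one return after session 4, when the first payment is already being processed, and another after session 9.
2. Add to the existing drop-out call a request to post the forms completed so far.
3. In the Phase III Data Analysis Plan, state that form return and satisfaction will be reported by completion status or by number of sessions attended.

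The cost is one extra stamped envelope per telehealth participant, one more request on a call already planned, and slightly more form tracking by staff. If all completed forms were retrieved when a Veteran stops, the loss described above would be zero.
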